1.3 Study variables

Primary variables:

- Mean change from baseline (BL) in SBP and DBP assessed at week 12 of the observational period.
- Mean change from BL in LDL-C assessed at week 12 of the observational period.

Secondary variables:

- Mean change from BL in SBP and DBP assessed at week 4 of the observation period.
- Proportion of the patients aged 18-64 years who reached SBP <140 mm Hg and DBP <90 mm Hg at week 4 of the observation period.
- Proportion of patients aged 18-64 years who reached target SBP <130 and \geq 120-mm Hg and DBP between 70 and79 mm Hg at week 12 of the observation period.
- Proportion of patients older than 65 years who reached SBP < 140 mm Hg and DBP < 90 mm Hg at week 4 of the observation period.
- Proportion of patients older than 65 years who reached SBP \leq 139 and \geq 130 mm Hg and DBP between 70 and79 mm Hg at week 12 of the observation period.
- Proportion of patients at very high CV risk who reached LDL-C decrease \geq 50% from BL and reached target < 1,4 mmol/l (55 mg/dl) or at week 12 of the observation period.
- Proportion of patients at high CV risk who reached LDL-C decrease \geq 50% from BL and reached target LDL-C < 1,8 mmol/l (70 mg/dl) at week 12 of the observation period.
- Proportion of patients at moderate CV risk who reached target LDL-C < 2,6 mmol/l (100 mg/dl) at week 12 of the observation period.
- Proportion of patients at different CV risk who reached both BP and LDC-C targets
- Proportion of patients aged 18-64 years at very high CV risk who reached SBP <130 and \geq 120 mm Hg and DBP between 70 and79 mm Hg at week 12 of the observation period in the subgroups of the patients receiving SPC of amlodipine/atorvastatin/perindopril in the following dosages 5;20;5 mg and 5;20;10 mg and 5;10;5 mg respectively;
- Proportion of patients older than 65 years at very high CV risk who reached SBP \leq 139 and \geq 130 mm Hg and DBP between 70 and79 mm Hg at week 12 of the observation period in the subgroups of patients receiving SPC of amlodipine/atorvastatin/perindopril in the following dosages 5;20;5 mg and 5;20;10 mg and 5;10;5 mg respectively
- Proportion of patients at very high CV risk who reached LDL_C decrease \geq 50% from BL and reached target <1,4 mmol/l (55 mg/dl) or at week 12 of the observation period in the subgroups of the patients receiving SPC of amlodipine/atorvastatin/perindopril in the following dosages 5;20;5 mg and 5;20;10 mg and 5;10;5 mg respectively;

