- Proportion of patients aged 18-64 years at high CV risk who reached SBP <130 and \geq 120 mm Hg and DBP between 70 and79 mm Hg at week 12 of the observation period in the subgroups of patients receiving SPC of amlodipine/atorvastatin/perindopril in the following dosages 5;20;5 mg and 5;20;10 mg and 5;10;5 mg respectively;
- Proportion of patients older than 65 years at high CV risk who reached SBP \leq 139 and \geq 130 mm Hg and DBP between 70 and79 mm Hg at week 12 of the observational period in the subgroups of patients receiving SPC of amlodipine/atorvastatin/perindopril in the following dosages 5;20;5 mg and 5;20;10 mg and 5;10;5 mg respectively;

- Proportion of patients at high CV risk who reached decrease of LDL-C from BL $\geq 50\%$ and reached target $<1,8$ mmol/l (55 mg/dl) at week 12 of the observation period in the subgroups of patients receiving SPC of amlodipine/atorvastatin/perindopril in the following dosages 5;20;5 mg and 5;20;10 mg and 5;10;5 mg respectively;
- Proportion of patients aged 18-64 years at moderate CV risk who reached SBP <130 and ≥ 120 mm Hg and DBP between 70 and 79 mm Hg at week 12 of observational period in the subgroups of patients receiving SPC of amlodipine/atorvastatin/perindopril in the following dosages 5;20;5 mg and 5;20;10 mg and 5;10;5 mg respectively;
- Proportion of patients older than 65 years at moderate CV risk who reached SBP ≤ 139 and ≥ 130 mm Hg and DBP between 70 and 79 mm Hg at week 12 of the observation period in the subgroups of patients receiving SPC of amlodipine/atorvastatin/perindopril in the following dosages 5;20;5 mg and 5;20;10 mg and 5;10;5 mg respectively;
- Proportion of patients at moderate CV risk who reached LDL-C $< 2,6$ mmol/l (100 mg/dl) at week 12 of the observation period in the subgroups of patients receiving SPC of amlodipine/atorvastatin/perindopril in the following dosages 5;20;5 mg and 5;20;10 mg and 5;10;5 mg respectively;
- Mean change from V0 in scores of the SF-36 questionnaire assessed at V1 and V2;
- Proportion of patients with high, moderate and low adherence to the treatment with SPC of amlodipine/atorvastatin/perindopril at V1 as compared to V0 via medication adherence scale;
- Proportion of patients with high, moderate and low adherence to the treatment with SPC of amlodipine/atorvastatin/perindopril at V2 as compared to V0 via medication adherence scale;
- Association between the fact of achieving target BP levels at week 12 and baseline BP and LDL-C levels;

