- Association between the fact of achieving target LDL-C level at week 12 and baseline BP and LDL-C levels as well as CV risk category;
- Association between the fact of achieving target BP and LDL-C levels at week 12 with the categories of CV risk, initial dosage of SPC amlodipine/atorvastatin/perindopril and adherence rate to the administered therapy with FDC.
- Association between patients' adherence to SPC amlodipine/atorvastatin/perindopril therapy at week 4 and week 12 and baseline BP level.
- Predictors for achieving target BP levels (i.e. smoking, sex, baseline SBP and DBP, duration of HTN, level of CV risk, duration of therapy, baseline LDL-C level, CAD diagnosis);
- Predictors for achieving target LDL-C levels (i.e. smoking, sex, baseline SBP and DBP, duration of HTN, level of CV risk, duration of therapy, baseline LDL-C level, CAD diagnosis).

2. Methods and documentation

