2.5 Therapeutic strategy during the study

2.5.1 Treatment with the studied drug

Amlodipine 5 mg + atorvastatin 10 mg + perindopril arginine 5 mg

Amlodipine 5 mg + atorvastatin 20 mg + perindopril arginine 5 mg

Amlodipine 5 mg + atorvastatin 20 mg + perindopril arginine 10 mg

This is non-interventional study that is observational by its nature. Therefore there will be no any assignments of subjects to a particular therapeutic strategies defined by this protocol. Decision to treat a patient with SPC of amlodipine/ atorvastatin/ perindopril should be at the discretion of a treating investigator and made in accordance to local standards and protocols.

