4.2 Statistical analysis

Due to the non-interventional nature of this study, statistical analysis will be carried out in descriptive and exploratory forms. All parameters will be analysed using descriptive statistics. For each parameter, the following will be specified: number of patients, mean value, standard error, minimum and maximum values, or proportion of each category. All composite endpoints will be listed and presented in visual form as graphs and in tables of parameters and their frequencies. For categorical variables, absolute values and rates in per cents be calculated. The calculations of relative rates will include only patients in whom values of the corresponding variables will be available.

Accepted level of significance

In all tests, a significance level of 0.05 will be used, and 2-sided statistical tests will be carried out.

Search statistical analysis will be performed in the following subgroups of patients:

- patients with stable CAD
- patients with diabetes mellitus type 1 or type 2
- patients with chronic kidney disease

All reports of adverse drug reactions (ARDs), adverse events (AEs), serious ADR/AE, and special situations will be encoded using MedDRA by the subcontractor, and the results will be listed and classified according to the System-Organ-Classes (SOCs). Descriptive statistics will be used.

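### The initial-dosage association with target attainment omits baseline BP and LDL-C although the protocol does not assign the strength, so the crude association can be confounded by starting level

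*Combined protocol and SAP*

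**What the plan says.** Section 2.5.1 lists three strengths and states that "there will be no any assignments of subjects to a particular therapeutic strategies defined by this protocol". It adds that "Decision to treat a patient with SPC of amlodipine/ atorvastatin/ perindopril should be at the discretion of a treating investigator". Sections 2.1 and 2.4.1 tie use to the approved Russian labelling. No section says how a strength is picked.

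Section 1.3 uses dose in two ways:

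- One association relates week-12 attainment of both targets "with the categories of CV risk, initial dosage of SPC amlodipine/atorvastatin/perindopril and adherence rate to the administered therapy with FDC".
- Nine target rates are reported by strength, "in the following dosages 5;20;5 mg and 5;20;10 mg and 5;10;5 mg respectively". They cover three CV-risk classes, each with BP at 18-64 years, BP over 65 years, and LDL-C.

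Baseline level appears elsewhere in 1.3. One item is "Association between the fact of achieving target BP levels at week 12 and baseline BP and LDL-C levels", and a parallel item covers the LDL-C target. Two predictor lists contain "smoking, sex, baseline SBP and DBP, duration of HTN, level of CV risk, duration of therapy, baseline LDL-C level, CAD diagnosis". Dose is in none of these.

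Section 4.2 says "statistical analysis will be carried out in descriptive and exploratory forms", sets two-sided tests at 0.05, and names no model or covariates.

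**The concern.** Most of the targets are absolute thresholds, so a patient who starts higher is less likely to be under the threshold at week 12, whatever the tablet. If prescribers tend to give one strength to patients with higher BP or LDL-C, a crude comparison of strengths mixes the effect of the tablet with the selection of patients. This is confounding by indication at the start of treatment. It would remain even if nobody changed dose later.

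At stake is how a listed result is read. The last secondary objective in 1.2 is to evaluate predictors of reaching targets, and 4.2 provides for significance tests. A dose association with a p-value is therefore foreseeable, and the plan has no caution against reading it as a dose effect.

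**Working it through.** **Figure taken from the plan.** The documents give no figure for the dose analyses. The completer count used in step 4 is the LDL-C sample size in 2.2, which reproduces: 1.01² × (2.326 + 1.282)² / 0.22² = 274.4, stated as 274.

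**Step 1: does any listed analysis hold both dose and baseline level?**

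| Analysis in 1.3 | Dose | Baseline BP or LDL-C as covariate |
|---|---|---|
| Attainment vs CV risk, initial dosage, adherence | yes | no |
| BP-target and LDL-C-target associations with baseline | no | yes |
| Two predictor lists | no | yes |
| Nine dose-split rates | yes | no (CV risk; age for BP) |

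None does.

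**Step 2: model with no true dose effect.**

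Inputs from the three-month observational study cited in 1.1:
- SBP 158.5 (SD 16.7) to 132.2 (SD 8.3) mmHg
- week-12 DBP 80.1 (SD 6.8) mmHg
- LDL-C 3.41 (SD 1.01) to 2.80 (SD 0.82) mmol/l

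Assumptions not in the documents:
- normal distributions
- baseline to week-12 correlation r = 0.5
- week-12 SBP-DBP correlation 0.5, with DBP linked to baseline only through SBP
- half the patients on a stronger tablet, chosen when (standardised baseline + k × independent noise) exceeds zero, with k = 3, 1 or 0 for weak, partial or strict dependence
- no stratification by CV risk or age
- the 50%-fall rates need both the fall and the threshold

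Baseline gap = 2 × √(2/π) × SD / √(1 + k²):
- SBP: 1.596 × 16.7 / √10 = 8.4; / √2 = 18.8; / 1 = 26.7 mmHg
- LDL-C: 0.51, 1.14 and 1.61 mmol/l

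Week-12 SBP gap = r × (baseline gap / 16.7) × 8.3 = 2.1, 4.7 and 6.6 mmHg.

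**Step 3: simulated attainment, stronger vs weaker tablet (%).**

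| Target | Weak | Partial | Strict | Gap (points) |
|---|---|---|---|---|
| BP 18-64 (SBP 120 to <130, DBP 70 to <80) | 16.2 vs 19.9 | 13.8 vs 22.3 | 11.8 vs 24.3 | about 4 to 13 |
| BP over 65 (SBP 130 to 139, DBP 70 to <80) | 16.5 vs 15.6 | 17.1 vs 15.1 | 17.6 vs 14.5 | about 1 to 3, reversed |
| LDL-C <2.6 | 35.4 vs 45.3 | 29.1 vs 51.5 | 24.2 vs 56.5 | about 10 to 32 |
| LDL-C <1.8 and 50% fall | 4.1 vs 4.6 | 3.8 vs 4.9 | 3.7 vs 5.1 | about 0 to 1 |
| LDL-C <1.4 and 50% fall | 2.2 vs 3.0 | 1.6 vs 3.5 | 1.0 vs 4.1 | about 1 to 3 |

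Sensitivity:
- With r from 0.3 to 0.7, the 18-64 gap under partial or strict dependence runs from 5 to 19 points.
- A second model used baseline SBP gaps of 5 to 15 mmHg, r of 0.2 to 0.6 and an equal DBP gap in SD units. It gives 1 to 9 points for 18-64. Over 65 it gives 0.2 to 1.9 points, not reversed.
- With LDL-C modelled as a percentage fall and baseline gaps of 0.25 to 1.0 mmol/l, the <2.6 gap is 5 to 34 points. The 50%-fall rates show almost no gap at a mean fall of 20%, close to the cited (3.41 − 2.80)/3.41 = 18%. At a mean fall of 45% the gap is 2 to 11 points.

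**Step 4: cell sizes.** Nine rates × three strengths = 27 proportions. With an even split of 274 completers (assumption), a BP cell has 274/18 ≈ 15 patients and an LDL-C cell 274/9 ≈ 30. At a 30% rate the 95% half-widths are 1.96 × √(0.21/15.2) ≈ 23 points and 1.96 × √(0.21/30.4) ≈ 16 points.

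**The case against.** The strongest reply is that the plan is descriptive, has no objective of comparing strengths, and is silent on a model rather than choosing an unadjusted one. That is fair for the nine rates, which are proportions within subgroups with no planned contrast. It does not cover the initial-dosage association, which is a listed variable. With no model named, the crude comparison is the default.

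Other parts of the reply stand:

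- Nothing in the documents says that higher baselines lead to a higher strength. The discretion clause in 2.5.1 concerns the decision to treat.
- The nine rates are already split by CV risk, and the BP rates by age. This removes part of the confounding but not all of it, because the Appendix 6 classes rest largely on disease history, diabetes, kidney function and SCORE.
- There are three strengths, not a weaker and a stronger one. Two share the same amlodipine and perindopril content and two share the same atorvastatin content, so BP and LDL-C bear on different contrasts. The two-group model only indicates size.
- The nine rates speak of patients "in the subgroups of the patients receiving SPC of amlodipine/atorvastatin/perindopril in the following dosages" stated, not of the initial dose, and 2.5.2 allows changes during follow-up.
- Cells of about 15 and 30 patients carry more noise than most of the modelled bias, so standardising the 27 proportions to a common baseline is not workable.

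A reader might infer that the stronger tablet will look less effective throughout. The documents do not support that. The direction depends on an undocumented prescribing pattern, and the over-65 gap reverses in one model. With an assumed real extra fall of 5/2.5 mmHg, the crude 18-64 difference still mostly favours the stronger tablet (true +7.2 points, crude +6.3 down to −0.7).

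**Conclusion.** The concern holds in a limited form. No listed analysis contains both dose and baseline BP or LDL-C, and the protocol does not assign the strength, so the crude initial-dosage association is open to confounding by starting level.

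If baseline influences the choice, the distortion could be material for the 18-64 BP band (about 4 to 13 points) and for LDL-C below 2.6 mmol/l (about 10 to 32 points). It is small for the over-65 band, where even the sign depends on how DBP is modelled. It is also small for the 50%-fall rates, unless the mean LDL-C fall is far above the cited 18%. All these sizes rest on the assumed dependence and correlation and ignore the existing stratification, so they show possible scale and are not forecasts.

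This should be fixed because adjustment costs almost nothing. The primary analyses and the sample size are not affected.

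**What to change.** In 1.3 and 4.2:

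1. Estimate the initial-dosage association with dose as a three-level factor. Adjust for baseline SBP and DBP (BP target) or baseline LDL-C (LDL-C target), age group and CV-risk class.
2. Keep the covariate set short. If about 18% of 274 completers reach the BP target (assumption, the 18-64 rate in the model), there are about 50 events. A model with all the listed predictors plus dose, about 12 parameters, would have about 4 events per parameter.
3. Beside each of the nine dose-split rates, print that dose group's baseline BP or LDL-C. Do not attempt baseline-standardised proportions in the 27 cells.
4. State whether the dose groups in those rates are defined by initial or current strength.
5. State that crude differences between strengths are descriptive and are not read as dose effects.

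The cost is SAP wording, a few model terms and extra table columns. The covariates are already collected under 2.7.2 and 2.7.4, and enrolment stays at 400.

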Appendix 5. Score Scale

Name: SCORE scale (Systematic Coronary Risk Evaluate)

Source: http://www.heartscore.org/ru_RU

Purpose: clinical tool for the assessment of the fatal CV event risk in the next 10 years. The scale has been developed for the countries with high CV mortality rate (including Russia) based on the following factors: age, smoking, SBP and total cholesterol levels. Level of HDL-C is not taken into consideration in this scale. It is recommended to use SCORE scale to assess risk in asymptomatic patients older than 40 years, without CVD, diabetes mellitus, chronic kidney disease or familial hypercholesterolemia

Interpretation:

Total CV risk according to SCORE scale:

Less than 1% — low.

1 - 4% — moderate.

5% - 9% — high.

> 10% - very high

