Appendix 7 Target office BP levels depending on age and concomitant diseases [15]

Age	Target office SBP mm Hg					Target office DBP mm Hg
	HTN	+ DM	+ CKD	+ CAD	+ Stroke ^a /TIA	
18 – 64 years	< 130 if tolerated but not <120	< 130 if tolerated but not <120	<140 to 130 if tolerated	< 130 if tolerated but not <120	< 130 if tolerated but not <120	70-79
65-79 years ^a	130-139 if tolerated	130-139 if tolerated	130-139 if tolerated	130-139 if tolerated	130-139 if tolerated	70-79
≥ 80 ^b	130-139 if tolerated	130-139 if tolerated	130-139 if tolerated	130-139 if tolerated	130-139 if tolerated	70-79

a Refers to the patients with the history of stroke and not to the BP measure in acute stroke.

b Target levels can be modified in elderly fragile patients.

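### The week-12 SBP target band depends on age, but the BP-target predictor and association analyses neither include age nor split by it; if pooled, a factor's effect can be diluted, cancelled or reversed

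*Combined protocol and SAP*

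**What the plan says.** Section 1.3 defines week-12 BP success separately by age. Below 65 years, SBP has to lie from 120 to under 130 mmHg. For the older group the limits are 130 and 139 mmHg. The DBP band, 70-79 mmHg, is common to both. These limits match Appendix 7, whose 65-79 row reads "130-139 if tolerated" in every SBP column. Eligibility runs from 18 to under 80 years (section 2.4.1), so both bands apply.

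Every BP-only proportion at week 12, including those by risk category and dose, is split by age. Three later items in the same section also take BP-target attainment as their outcome, and none of these is split.

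- The first is worded "Association between the fact of achieving target BP levels at week 12 and baseline BP and LDL-C levels".
- The second relates the combined BP and LDL-C target to risk category, starting dose and adherence.
- The third is the predictor list, which opens "Predictors for achieving target BP levels (i.e. smoking, sex, baseline SBP and DBP, duration of HTN, level of CV risk, duration of therapy".

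Counting SBP and DBP separately, the full list holds nine factors, and none of them is age. Age enters only through the risk category, since Appendix 5 describes SCORE as "based on the following factors: age, smoking, SBP and total cholesterol levels". Section 4.2 gives no model, age stratum or interaction for these items. Its exploratory subgroups are CAD, diabetes and CKD.

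**The concern.** The two SBP bands are adjacent and do not overlap. An analysis of a single attained/not-attained outcome across all ages therefore mixes two definitions of success. Where achieved SBP lies between the middles of the two bands, lowering it moves younger patients into their band and older patients out of theirs. A pooled estimate then describes neither group. Identifying predictors of reaching BP targets is a stated secondary objective (section 1.2), and a real predictor such as better adherence could look weak, absent or harmful. Factors that go with age, such as CAD or duration of hypertension, could also pick up the difference between the bands.

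**Working it through.** The plan gives no figure for these analyses, so there is none to reproduce. The completer count used at the end does reproduce: 1.01² × (2.326 + 1.282)² / (0.44 − 0.22)² ≈ 274.4, stated as 274 (section 2.2).

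**Inputs.** Month-3 office BP of 132.2 (SD 8.3)/80.1 (SD 6.8) mmHg, from the observational study described in section 1.1. Bands from section 1.3, taken to whole mmHg: SBP 119.5-129.5 (younger) and 129.5-139.5 (older), DBP 69.5-79.5. Assumptions not in the documents: normal distributions, the same BP distribution in both age groups, SBP-DBP correlation r, share of older patients, and a factor worth 5 mmHg of SBP.

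**Step 1: SBP part alone.** P(in band) = Φ((upper − m)/8.3) − Φ((lower − m)/8.3).

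- Younger, m = 132.2: Φ(−0.325) − Φ(−1.530) = 0.3725 − 0.0630 = 30.9%.
- Younger, m = 127.2: Φ(0.277) − Φ(−0.928) = 0.6092 − 0.1768 = 43.2%. Odds ratio (OR) 1.70.
- Older, m = 132.2: Φ(0.880) − Φ(−0.325) = 0.8104 − 0.3725 = 43.8%.
- Older, m = 127.2: Φ(1.482) − Φ(0.277) = 0.9308 − 0.6092 = 32.2%. OR 0.61.
- Pooled OR: 1.24, 1.01 and 0.83 with 30%, 50% and 70% older patients.

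**Step 2: where directions oppose.** P(in band) peaks when the mean is at the band midpoint: (119.5 + 129.5)/2 = 124.5 and (129.5 + 139.5)/2 = 134.5. Between these, a small fall in SBP helps the younger and hurts the older. Above 134.5 it helps both; below 124.5 it hurts both. The expected 132.2 lies inside the interval. Starting higher gives dilution:

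| Mean SBP | OR younger | OR older | Pooled OR, equal groups |
|---|---|---|---|
| 137.2 to 132.2 | 2.35 | 1.02 | 1.42 |
| 140 to 135 | 2.70 | 1.39 | 1.66 |

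**Step 3: joint SBP and DBP target.** Bivariate normal, r = 0.5, from 132.2/80.1.

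| Change | Younger | Older | Pooled, equal groups |
|---|---|---|---|
| SBP −5, DBP unchanged | 16.9% to 20.4% (OR 1.26) | 16.5% to 9.0% (OR 0.50) | 16.7% to 14.7% (OR 0.86) |
| SBP −5, DBP −2.5 | 16.9% to 24.5% (OR 1.59) | 16.5% to 13.3% (OR 0.78) | 16.7% to 18.9% (OR 1.16) |

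**Step 4: sensitivity to the older share.** With DBP unchanged and 30% older patients, the pooled rate is nearly flat (16.8% to 17.0%). With DBP also down 2.5 mmHg and 70% older, it is flat again (16.6% to 16.7%). Over r from 0 to 0.6, exact cancellation falls at about 27-51% older with DBP unchanged. With a DBP fall of 2.2 mmHg, which keeps the 26.3 : 11.6 ratio of falls in that study, it falls at about 63-80%.

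**Step 5: the band as a confounder.** At identical BP, the SBP part is met by 43.8% of older and 30.9% of younger patients (OR 1.74). For the joint target the gap is 17.8% against 12.5% at r = 0, and almost nil at r = 0.5 (16.5% against 16.9%).

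**Step 6: events available.** 0.167 × 274 ≈ 46 successes, or about 23 per band if split equally. For nine factors that is 23/9 ≈ 2.6 per factor.

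**The case against.** The strongest reply is that nothing in the plan says these analyses are pooled. Section 4.2 promises only descriptive and exploratory work, and the BP-only proportions are split by age, so an analyst might carry the split over. That stands as far as it goes: the defect is an unspecified stratification, not a declared wrong model.

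A reader might infer more, in three ways that the documents do not support.

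- *That pooling will cancel or reverse the effect, so that a BP-lowering factor looks harmful.* This needs achieved SBP between about 124.5 and 134.5 mmHg, a particular older share (not given), and little movement in DBP. In the cited study SBP and DBP fell together. With DBP also falling and equal groups, the pooled result points the right way and is merely diluted.
- *That the two age groups share one BP distribution.* This is a working assumption. If older patients start at 137.2/80.1, a 5/2.5 mmHg fall raises their joint attainment from 20.4% to 22.0%, and the directions no longer oppose.
- *That the predictor list is closed because of the abbreviation that introduces it.* The protocol uses the same abbreviation for examples elsewhere (planned surgery in section 2.4.2, concomitant medication in section 2.7.4), so age is not shown to be excluded.

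In addition, the predictor item names no visit. I read it as week 12, as the association items state. At week 4 both age groups share the limits <140 and <90 mmHg, and the problem would not arise.

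**Conclusion.** The point holds in conditional form. Age decides which SBP band counts as success, and the three analyses of BP-target attainment do not take it into account. At the BP level quoted in section 1.1, and with equal distributions in both groups, the age-specific effects lie on opposite sides of 1. With equal groups and r = 0.5, the pooled joint rate then ranges from a 2.0-point fall (DBP unchanged) to a 2.2-point rise (DBP down 2.5 mmHg). Neither describes either age group. Dilution is the usual result when DBP falls too; cancellation or reversal is possible but not shown to be likely. Confounding by age-related factors is clear for the SBP part and may be small for the joint target. The primary endpoints are unaffected. This is a cheap improvement to an exploratory secondary objective; confidence is moderate.

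**What to change.** In sections 1.3 and 4.2, state that the BP-target predictor and association analyses, including the one on the combined BP and LDL-C target, will be run separately by age band or with an age-band-by-predictor interaction. Adding age as a main effect is not enough, because a single common slope would still average opposing effects. Do not report a pooled coefficient on its own. Name the visit for the predictor item. Also reconcile the age wording, since section 1.3 has 18-64 and older than 65 while Appendix 7 has 65-79, so that each patient falls in one band.

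Age is already available from eligibility and V0 demographics, so no new data or visits are needed. The real cost is precision: about 23 successes per band allows only a few predictors to be fitted jointly, and a full interaction model is equally sparse. Pre-specify a short list or present one-factor estimates with confidence intervals. That is acceptable for an exploratory objective.
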